4.3 ANALYSIS OF STUDY CONDUCT

The number of patients randomized will be tabulated by region, country, study site, and treatment arm. Patient disposition (the number of patients randomized, receiving at

least one dose of study treatment [lampalizumab or sham], completing study treatment [through Week 48 or Week 96, as appropriate], and completing study visit assessments [through Week 48 or Week 96, as appropriate]) and time on study will be tabulated by treatment arm in the overall and biomarker patient groups. Reasons for premature discontinuation from study treatment and reasons for premature discontinuation from study assessment visits will be summarized. Eligibility criteria deviations, dosing errors, and other major protocol deviations will be summarized. All summaries for analysis of study conduct will be produced based on the primary 48-week analysis data, and also based on the final study data as appropriate.

4.4 ANALYSIS OF TREATMENT GROUP COMPARABILITY

Demographic and baseline characteristics such as age, sex, race, ethnicity, and baseline ocular characteristics (such as baseline GA area, location of GA lesion, GA lesion multifocality, baseline BCVA, baseline LLVA, and history of glaucoma, glaucoma suspect, and ocular hypertension) will be summarized for the ITT population by treatment arm in the overall and biomarker patient groups using descriptive statistics.

4.5 EFFICACY ANALYSIS

Efficacy analyses will be based on the ITT patient population or microperimetry-analysis population, as appropriate (Section 4.1.1), with patients grouped according to the treatment assigned at randomization. Available data from all randomized and treated patients regardless of adherence to the protocol will be included in the efficacy analyses; this includes data from patients who discontinued study drug early but continued with study assessments.

Unless otherwise noted, hypothesis testing and estimation of treatment effects will be performed with a regression model that includes data from all three treatment arms (sham pooled, lampalizumab Q4W, and lampalizumab Q6W). When analyzing data by biomarker group, separate regression models will be fit for the biomarker-positive and biomarker-negative patient groups (as defined in Section 2.2). All hypothesis tests for efficacy endpoints will be two-sided.

Unless otherwise noted, analyses of efficacy endpoints (primary, secondary, and exploratory) in the overall patient population will be adjusted for the following randomization stratification factors and baseline covariates:

- Biomarker status (positive vs. negative, as determined by the cobas[®] CFI Profile CTA)
- Baseline BCVA ETDRS chart Snellen equivalent (20/50 or better vs. worse than 20/50)
- Sex (male vs. female)
- Baseline GA lesion contiguity (multifocal vs. non-multifocal)

- For efficacy endpoints based on GA area and microperimetry assessments (e.g. number of absolute scotomatous points) only.
- Baseline GA lesion location (subfoveal vs. non-subfoveal)
 - For efficacy endpoints based on GA area, microperimetry assessments (e.g. number of absolute scotomatous points), and visual acuity (BCVA or LLVA) only.

Analyses of efficacy endpoints performed by biomarker group will include the above listed randomization stratification factors and baseline covariates with the exception of biomarker status.

All patients are expected to have the randomization stratification factors and baseline covariates that are specified above. One exception is that a small number of patients do not have a valid baseline BCVA score recorded per the corresponding electronic case report form. In order to include these patients in the efficacy analyses based on regression modeling with covariate adjustment, the BCVA category (20/50 or better vs. worse than 20/50) captured in the IxRS will be used.

For endpoints that are defined in terms of change from baseline, patients who do not have a baseline value reported for a particular assessment will be excluded from the change-from-baseline analyses for that assessment. Similarly, in general, patients who do not have at least one post-baseline value reported for a particular assessment will be excluded from the change from baseline analyses for that assessment. For selected endpoints, sensitivity analyses that include patients without observed post-baseline values will be performed.

For continuous outcomes, a data-as-observed approach with a mixed-effect model repeated measures (MMRM) will be used to handle missing data, which assumes that the missing data are missing at random (MAR). For binary outcomes, analysis of the outcome at a specific time point will be based on observed data, unless otherwise noted. Study discontinuations and the reasons for study discontinuations will be summarized by treatment arm (see Section 4.3) to evaluate the potential impact of missing data on the results. In addition, a number of sensitivity analyses to assess the robustness of the primary analysis results to missing data assumptions will be performed.

For patient-reported outcome measures (e.g., NEI VFQ-25), there are two types of missing data: missing at the form level and missing at the item level. Missing form level data will be handled as described above. Missing item values will follow the rules for scoring and handling of missing item-level data as described in the user's manual.

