3.1.1 Planned Total Sample Size

Approximately 936 patients (188 biomarker-positive patients per treatment group [lampalizumab Q4W, lampalizumab Q6W, and pooled sham] and 124 biomarker-negative patients per treatment group [lampalizumab Q4W, lampalizumab Q6W, and pooled sham]) will be enrolled in the study at approximately 140 sites located globally.

At selected sites, microperimetry assessment will be performed on a subgroup of approximately 138 CFI profile biomarker-positive patients and approximately 90 CFI profile biomarker-negative patients.

At selected sites, serial ECG evaluations will be performed on approximately 100 study patients, independent of CFI profile biomarker status (see Section 4.5.7).

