4.2 METHOD OF TREATMENT ASSIGNMENT AND MASKING

4.2.1 Treatment Assignment

After written informed consent has been obtained, all patients will receive a screening number assigned through the Interactive Voice and Web Response Systems (IxRS). A patient must satisfy all eligibility criteria (see Sections 4.1.1 and 4.1.2) at both the screening and the Day 1 visit (first study treatment) prior to randomization. As part of the screening process, the central reading center (masked to patient treatment assignment) will evaluate FAF images, CFP, and FA to provide an objective, masked assessment of patient eligibility. After all patient eligibility requirements are confirmed, site personnel will contact the IxRS on Day 1 visit for assignment of a patient identification number (a separate number from the screening number). Patients will be randomized in a 2:1:2:1 ratio to one of the study treatment arms (lampalizumab Q4W, sham Q4W, lampalizumab Q6W, or sham Q6W). The study treatment kit number will be also assigned by IxRS at that time. Patients will be randomized on the same day the study treatment is to be initiated (Day 1 visit).

Randomization will be stratified by biomarker status (positive vs. negative, as determined by the investigational cobas[®] CFI Profile assay), baseline BCVA ETDRS chart Snellen equivalent (20/50 or better vs. worse than 20/50), sex (woman vs. man), and microperimetry eligibility (yes vs. no). A permuted-block randomization method will be used to obtain an approximately 2:1 ratio between lampalizumab and sham arms for each dosing frequency within each stratum.

Once the study randomizes the allotted number of CFI profile biomarker-negative or CFI profile biomarker-positive patients (see [Figure 2](#)), the additional screened patients who would have been randomized in the already-filled biomarker arms will be screen-failed.

Patients and all study site personnel will be masked for CFI profile biomarker status until study completion. Sponsor study team members who have direct contact with study sites will be masked to CFI profile biomarker status, but team members who do not interact with study sites may review individual patient CFI profile biomarker status.

Details of the randomization procedure will be described in the Statistical Analysis Plan (SAP).

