6.4.1 Primary Efficacy Endpoint

The primary efficacy endpoint is the mean change in GA area from baseline at 1 year (Week 48) as assessed by FAF.

For each biomarker group, the mean change in GA area from baseline will be compared between each active treatment arm and the pooled sham arm by use of a linear mixed-effect model. The primary analysis will be based on all available data up to 1 year, with no imputation for missing data.

The dependent variable in the mixed-effect model is the change from baseline in GA area at post-baseline visits, up to 1 year, and the independent variables are the randomized treatment group, time, treatment-by-time interaction, baseline GA area, and the randomization stratification factors of (biomarker status, baseline BCVA ETDRS chart Snellen equivalent category, sex, and microperimetry eligibility). The mixed-effect model will assume an unstructured covariance structure. If there are convergence problems with the model, then a compound symmetry covariance structure will be fitted. A similar model with two additional independent variables, the biomarker status and the interaction of treatment and biomarker status, will be used to evaluate the predictive value of the genetic-defined biomarker. Also, for patients treated with sham, a comparison of change from baseline in GA area between biomarker-positive patients and biomarker-negative patients will be performed to evaluate the prognostic value of the CFI profile biomarker.

To manage the type I error of 0.0495 (two-sided), testing of the primary endpoint will be conducted in the following sequential order:

- Step 1: lampalizumab Q4W CFI profile biomarker-positive group versus pooled sham CFI profile biomarker-positive group

If there is no statistically significant difference found in this treatment comparison at the significance level of 0.0495, then the test for the next stage will not be considered statistically significant regardless of the p-value.

- Step 2: lampalizumab Q4W CFI profile biomarker-negative group versus pooled sham CFI profile biomarker-negative group, and lampalizumab Q6W CFI profile biomarker-positive group versus pooled sham CFI profile biomarker-positive group

[figure not shown]

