3. STUDY CONDUCT

3.1 RANDOMIZATION

Patients are randomized to the treatment arms through an IxRS. After all patient eligibility requirements are confirmed at both the screening and Day 1 visit, patients are randomized in a 2:1:2:1 ratio to one of four arms (10 mg lampalizumab Q4W, sham Q4W, 10 mg lampalizumab Q6W, or sham Q6W). Study treatment is to be initiated on the same day that the patient is randomized (Day 1 visit).

Randomization is stratified by biomarker status (positive vs. negative, as determined by the cobas[®] CFI Profile CTA), baseline BCVA ETDRS chart Snellen equivalent (20/50 or better vs. worse than 20/50), sex (male vs. female), and microperimetry eligibility (yes vs. no). A permuted-block randomization method is used to obtain an approximately 2:1 ratio between lampalizumab and sham arms for each dosing frequency within each stratum.

Once the study randomizes the allotted number of CFI profile biomarker-positive or CFI profile biomarker-negative patients necessary to achieve the targeted 1.5:1 ratio for biomarker groups (see Section 2.2), the additional screened patients who would have been randomized in the already filled biomarker group will be screen-failed.

Following randomization and during the treatment period, the IxRS makes study treatment kit assignments.

Patient randomization and study treatment kit assignments are verified on an ongoing basis by an external and independent data coordinating center (iDCC). The iDCC independently reviews the logs to ensure that randomization and kit assignments are conducted correctly by the IxRS.

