4.1.3 Microperimetry-Analysis Population

Microperimetry assessments were performed on a subset of patients at selected study sites only. The microperimetry analysis population will be comprised of all ITT patients with microperimetry assessments who met the microperimetry eligibility criteria as evaluated by the central reading center, and validation checks will be applied to identify microperimetry assessments of sufficient quality for inclusion in the analysis. For analyses based on this patient population, patients will be grouped according to the treatment assigned at randomization. Due to the smaller sample size enrolled than anticipated, statistical inferences for efficacy endpoints based on microperimetry assessments will be based on pooled data from Studies GX29176 and GX29185.

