- **Tipping Point Analysis Method.** The tipping point analysis method will be implemented for each active treatment arm and by biomarker status under the MNAR assumption by searching for a tipping point that reverses the conclusion regarding positive treatment effect. For the active treatment arms, monotone missing data will be imputed based on the available values (observed values plus values imputed for non-monotone missing data) in the same treatment arm with a shift parameter added to the imputed values. Multiple imputation will be implemented on the differences between two consecutive visits, with the shift parameter allocated to the missing data point(s) proportionally across the 48 weeks. (e.g. For a shift parameter of 1 mm², incremental shifts of 0.5 mm², 0.25 mm², and 0.25 mm² would apply to Week 24, Week 36, and Week 48, respectively.) The range of the shift parameters will depend on the observed treatment effect, i.e., the difference in the change of GA area from baseline at Week 48 between lampalizumab and the pooled sham arms. The precision of the tipping point will be at one decimal point. A tipping point may not exist within reasonable clinical assumptions.

Additional Sensitivity Analyses:

Moreover, the following sensitivity analysis will be conducted based on observed data for the primary endpoint:

- **ANCOVA:** Comparison of the mean change in GA area from baseline at Week 48 between each lampalizumab arm (Q4W or Q6W) and the pooled sham arm using an analysis of covariance (ANCOVA) regression model with change from baseline at Week 48 as the response variable and independent variables for treatment arm, baseline GA area, and the randomization stratification factors and baseline covariates as described in Section 4.5.
- **Van Elteren Test:** Comparison of the distribution of change in GA area from baseline at Week 48 between each lampalizumab arm (Q4W or Q6W) and the pooled sham arm respectively, using the non-parametric Van Elteren test stratified by baseline GA area ($\leq 4DA$, $> 4DA$, where 1 disc area [DA] = 2.54 mm²) and the randomization stratification factors and baseline covariates as described in Section 4.5.

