All hypotheses for the key secondary endpoints will be tested for significance at the study level, except for H₀₅. The secondary endpoint of number of absolute scotomatous points will be based on the microperimetry-analysis population, which is estimated to be 10-15% of the total ITT population. Microperimetry was assessed in a subset of patients at selected study sites only. For this secondary endpoint, data from both Studies GX29176 and GX29185 will be combined to achieve a sample size sufficient to evaluate and test for treatment differences with a reliable level of precision.

As a consequence of this, for analyses of secondary efficacy endpoints at the individual study level:

- For H₀₅, the study-level p-value will be presented. However, interpretation of significance in a confirmatory manner will be based on the analysis of pooled data from Studies GX29176 and GX29185.
- H₀₆ will be tested in a confirmatory manner at the study-level if and only if, based on an analysis of pooled data from Studies GX29176 and GX29185, H₀₅ is rejected (i.e., pooled analysis $p \leq 0.0496$).
- H₀₇ will be tested in a confirmatory manner at the study-level if and only if H₀₆ is rejected at the study-level

As noted above, significance testing for H₀₅ will not be done at the study level, but rather interpretation of significance in a confirmatory manner will be based on the analysis of pooled data from Studies GX29176 and GX29185 for the microperimetry-based endpoint.

All hypothesis tests for the secondary endpoints will be on the basis of a two-sided alpha level of 0.0496.

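### Randomization is stratified by microperimetry eligibility, but SAP 4.5 drops that factor from the covariate list without a reason; if it is prognostic, the linear ITT models are slightly conservative

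*SAP*

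**What the plan says.** SAP 3.1 names four stratification factors, ending with "sex (male vs. female), and microperimetry eligibility (yes vs. no", and uses permuted blocks within each stratum. Protocol 4.2.1 has the same four, ending with "sex (woman vs. man), and microperimetry eligibility (yes vs. no". The mixed model in Protocol 6.4.1 adjusts for biomarker status and "baseline BCVA ETDRS chart Snellen equivalent category, sex, and microperimetry eligibility".

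SAP 4.5 states that efficacy analyses "in the overall patient population will be adjusted for the following randomization stratification factors and baseline covariates". The list that follows has biomarker status, baseline BCVA category, sex, lesion contiguity and lesion location. Microperimetry eligibility is absent. The primary MMRM (SAP 4.5.1.1), the ANCOVA and Van Elteren test (4.5.1.4), the slope model (4.5.1.5) and the secondary and exploratory models (4.5.2, 4.5.3) all point back to this list, so the factor is not restored anywhere.

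SAP 1 says that the SAP supersedes the protocol's analysis plan, but the change it singles out is to the hypotheses and their order. SAP 4.1.3 notes the microperimetry shortfall ("Due to the smaller sample size enrolled than anticipated") only as the reason for pooling with Study GX29185. By contrast, SAP 4.5.2 does explain why BCVA category is left out where continuous BCVA is in the model.

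**The concern.** Stratified randomization forces balance on the factor. If the factor also predicts outcome beyond the covariates already in the model, the treatment difference varies less from trial to trial than a model without the factor assumes. In a linear model that variance stays in the error term, so the reported standard error is too large and the test runs below its nominal level.

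This bears on the linear models of continuous ITT endpoints: the primary MMRM, the ANCOVA, and the MMRMs for LLVA, BCVA, reading speed and the questionnaires. It has no bearing on models restricted to the microperimetry-analysis population, where eligibility hardly varies. The standard-error argument does not carry over to the logistic models.

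What is at stake is a little power. H01 opens the fixed sequence and by itself defines a positive study (SAP 4.5.1), so that is where lost precision would matter most. There is also a transparency point: a covariate that the protocol specified for the primary model has gone without explanation.

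**Working it through.** **Inputs from SAP 2.3.2:** 312 patients per lampalizumab arm against 312 pooled sham, 15% dropout, SD 1.53 mm², target difference 0.42 mm², two-sided alpha 0.0496 (critical value 1.9634).

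**The plan's own figure.** n = 312 × 0.85 = 265.2 per arm. SE = 1.53 × √(2/265.2) = 0.1329. Power is 88.3% by the noncentral t (SAP: 88%), and the minimum detectable difference is 1.9634 × 0.1329 = 0.26 mm² (SAP: 0.26). Both reproduce.

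**Assumed inputs.** The documents give neither the share of eligible patients nor the factor's prognostic effect.

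- Share p: SAP 4.5.2.1 describes the microperimetry-analysis population as one "which is estimated to be 10-15% of the total ITT population". The midpoint, 12.5%, is used as a proxy for the eligible stratum. As an upper case, Protocol 3.1.1 planned "approximately 138 CFI profile biomarker-positive patients and approximately 90 CFI profile biomarker-negative patients", so (138 + 90)/936 = 24.4%. Fewer were enrolled.
- Residual difference d in Week 48 GA change between eligible and ineligible patients, after the other covariates: 0.25, 0.5 or 1.0 mm². The last is nearly half the assumed mean growth of 2.08 mm² and is an extreme.

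**Formulas**

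- Share of variance explained: R² = p(1 − p)d²/1.53²
- Standard-error inflation: k = 1/√(1 − R²)
- Type I error with the factor omitted: 2(1 − Φ(1.9634k))
- Power with the factor included: noncentral t with SD 1.53/k. Power with it omitted: same noncentrality, critical value multiplied by k.

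Example, p = 0.125 and d = 0.5: R² = 0.125 × 0.875 × 0.25/2.3409 = 0.0117; k = 1.0059; type I error = 2(1 − Φ(1.975)) = 0.0483.

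| p | d (mm²) | R² | SE too large by | Type I error, omitted | Power omitted | Power included |
|---|---|---|---|---|---|---|
| 12.5% | 0.25 | 0.29% | 0.15% | 0.0493 | 88.37% | 88.42% |
| 12.5% | 0.5 | 1.17% | 0.59% | 0.0483 | 88.47% | 88.69% |
| 12.5% | 1.0 | 4.67% | 2.42% | 0.0443 | 88.89% | 89.76% |
| 24.4% | 0.25 | 0.49% | 0.25% | 0.0490 | 88.39% | 88.49% |
| 24.4% | 0.5 | 1.97% | 1.00% | 0.0474 | 88.57% | 88.94% |
| 24.4% | 1.0 | 7.87% | 4.18% | 0.0408 | 89.28% | 90.72% |

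Across the SAP's 10–15% range, the power gains from including the factor are 0.05–0.07, 0.18–0.26 and 0.72–1.02 points for the three values of d.

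**Simulation.** The formula assumes that the arms stay exactly balanced on the factor among analysed patients. A null simulation with 936 patients, 16 strata, permuted blocks of 6 (block size assumed), 15% random dropout and p = 12.5% (40,000 trials per case, Monte Carlo error about 0.001) gave type I error, omitted against included, of 0.0492 and 0.0491 (d = 0.25), 0.0486 and 0.0491 (d = 0.5), and 0.0457 and 0.0491 (d = 1.0). A larger run at d = 1.0 (200,000 trials, 265 per arm) gave 0.0455 against 0.0507, and power of 89.0% against 89.9%. The direction is confirmed, and the formula somewhat overstates the loss in type I error.

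All of this approximates the Week 48 analysis by an ANCOVA. The MMRM would enter the factor as a single effect across visits, so its gain may be smaller.

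**The case against.** The strongest reply is that this hardly matters. Eligibility depends on being at a selected site and being able to do the test reliably (Protocol 4.1.3), which says little about lesion growth. Any link through fixation may already be captured by lesion location, BCVA category and baseline GA area, all of which are in the primary model. No document shows that the factor is prognostic. At a residual difference of 0.5 mm² or less the effect is barely visible in simulation, random dropout loosens the balance that the formula relies on, and the 24.4% share reflects a plan that was not met. The SAP is also entitled to revise the protocol's covariates, and any error is on the conservative side.

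Most of this stands, and it limits the size of the point. It does not remove it: the claim is conditional on prognostic value, the SAP gives no reason for the omission, and low enrolment is not an evident one. At 10–15% of 936, some 94 to 140 patients are eligible, ample for one binary main effect in the overall linear models.

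**Conclusion.** The point holds and is minor. A factor used to stratify randomization, and included in the protocol's primary model, is missing from SAP 4.5 with no reason given. If it is prognostic beyond the other covariates, the linear ITT analyses are slightly conservative: at a 12.5% share, a loss of 0.06 to 0.2 points of power for residual differences of 0.25 to 0.5 mm², and 0.9 points at the extreme of 1.0 mm². These figures rest on an assumed prognostic effect and on the microperimetry-analysis population standing in for the eligible stratum. A positive result would not be called into question by the omission.

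**What to change.** Before unmasking for the Week 48 analysis, add one entry to the SAP 4.5 list:

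> Microperimetry eligibility (yes vs. no, as recorded in the IxRS): for MMRM, ANCOVA and slope-model analyses of continuous endpoints in the ITT population only.

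In the slope model the term is there for consistency; a main effect shifts the level of GA area, not its growth rate.

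Leave the factor out of models restricted to the microperimetry-analysis population, sparse subgroup models, logistic models with low response rates, and the sensitivity analysis "using the non-parametric Van Elteren test stratified by baseline GA area". That test already crosses six binary factors, 2⁶ = 64 cells. A seventh would make 128, and at a 10–15% share of a 624-patient comparison each eligible cell would hold about 0.10 × 624/64 = 1.0 to 0.15 × 624/64 = 1.5 patients, fewer after dropout.

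The cost is one line of text and one model term, using a variable that the IxRS already holds; SAP 4.5 already draws on the IxRS for BCVA category. If the sponsor prefers the list as it stands, the SAP should say why a stratification factor was dropped.
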